Following confirmation of inclusion/exclusion criteria and upon histological confirmation of NASH by liver biopsy, patients will be enrolled into the study.

Eligible patients will be randomly assigned to receive Saroglitazar Magnesium 2 mg or 4 mg or placebo in a 2:2:1 ratio for 24 weeks.

Upon completion of 24 weeks of treatment, liver biopsy will be performed and the NAFLD Activity Score recorded (Appendix 2).

	Approved by: [name] [name]	Protocol No.: SARO.17.004.02.PROTOCOL Version No.: 2.0
---	---	---

 Zydus Discovery DMCC	CLINICAL TRIAL PROTOCOL Saroglitazar Magnesium – Phase 2 SARO.17.004	CONFIDENTIAL Page 7 of 76
--	---	--

The scheduled visits during this study will be as follows:

- Visit 1: Screening Visit [-4 Week (-28 Days)],
- Visit 2: Enrollment Visit (Day 1± 7 Days /Week 0),
- Visit 3: Day 43/Week 6 ± 7 Days,
- Visit 4: Day 85/Week 12 ± 7 Days,
- Visit 5: Day 127/Week 18 ± 7 Days,
- Visit 6: Day 169/Week 24 ± 7 Days,
- Visit 7: Follow-up Visit: Day 197/Week 28 ± 7 Days,

If the patient has consumed restricted medications but is otherwise considered eligible to be enrolled in this study by the PI, a minimum of 1 month wash out period will be instituted before the screening visit. All unscheduled visits will be reported in the Case report form.

Patients will be advised to follow a stable lifestyle. No change in the intensity of lifestyle (Diet/Exercise) will be allowed during the period of study. Patient will be monitored for safety and efficacy parameters as per Visit Schedule.

If further investigations are required in case of any AE, Investigator is advised to assess the AE and take necessary action. Patients are advised to contact the Investigator for any complaints.

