#### 4 STUDY POPULATION

Subjects clinically suspected of NASH and having laboratory evidence of abnormally elevated liver function tests (LFT) suggestive of NASH and confirmed histologically by biopsy will be recruited for the study. The histological evidence of NASH is defined as NAS  $\geq 4$  with a minimum score of 1 for all of its three components [steatosis, hepatocyte ballooning and lobular inflammation].

If the subject has consumed restricted medications but is otherwise considered eligible to be enrolled in this study by the Investigator, then a minimum of 1 month wash out period will be instituted before the screening visit.

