##### 4.2 INCLUSION CRITERIA

1. Patients able to provide written informed consent for participation in this trial.
2. Males or females, 18 to 75 years of age, both inclusive.
3. Female must be either of non-child bearing potential (surgically sterilized at least 6 months prior to screening or postmenopausal) or using one or more methods of contraception.
4. Histologic confirmation of NASH without cirrhosis (fibrosis stage 0, 1, 2, or 3) from liver biopsy performed either during the screening period or no more than 6 months prior to the first visit, with a NAS of  $\geq 4$  and a score of at least 1 in each (steatosis scored 0-3, ballooning scored 0-2 and lobular inflammation scored 0-3). If biopsy was performed within 6 months of screening, the slides, biopsy material or block should be available for baseline documentation. Such patients, whose historical biopsy report is available, should not use medications suspected of having an effect on NASH for at least 3 months prior to the screening.
5. BMI  $\geq 25$  kg/m^2.

	Approved by: [name] [name]	Protocol No.: SARO.17.004.02.PROTOCOL Version No.: 2.0
---	---	---

 Zydus Discovery DMCC	CLINICAL TRIAL PROTOCOL Saroglitazar Magnesium – Phase 2 SARO.17.004	CONFIDENTIAL Page 28 of 76
--	---	---

6. For hypertensive patients, blood pressure must be controlled by a stable dose of antihypertensive medications for at least 3 months prior to screening (and the stable dose can be maintained throughout the study)
7. Patients with type 2 diabetes mellitus may be included if they fulfil the following criteria;
  - a. Stable therapeutic regimen as defined by no changes in oral agents or dose for at least 3 months before screening and the stable dose can be maintained throughout the study.
  - b. HbA1c  $\leq$  9.5%.
8. Patients agree to comply with the study procedure.

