## 5.8 CONCOMITANT MEDICATIONS AND OTHER RESTRICTIONS

### 5.8.1 Previous and Concomitant Medications

[figure not shown]
Any medication the subject takes other than the study drug, including herbal and other non-traditional remedies, is considered a concomitant medication. All concomitant medications and any changes in the dosage or regimen of a concomitant medication for the 30 days preceding Visit 1 until the end of the study (i.e., the safety follow-up) must be recorded in the CRF.

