## 7 INVESTIGATIONAL PLAN

### 7.1 STUDY DESIGN AND PLAN

This is a randomized, double-blind, placebo-controlled, study to evaluate safety and efficacy of Saroglitazar Magnesium 2 mg and 4 mg in patients with NASH. This study will be initiated after obtaining the approvals of Institutional Ethics Committee/Institutional Review Board (IEC/IRB) and the local Regulatory Authority.

It is the responsibility of the Principal Investigator (PI) to ensure that the study is conducted in accordance with the protocol, International Council for Harmonisation Good Clinical Practice, and all applicable regulatory requirements. Informed consent will be obtained before the start of any study related procedures.

[figure not shown]
As per the contemporary guidelines, the PI shall maintain Source Documents (SD), Site Master File (SMF), Informed Consent Forms/Documents (ICF/ICD) and other logs/forms during the conduct of a study.

All laboratory reports should be reviewed by the PI and/or his/her designee and any abnormal findings should be addressed. All protocol deviations occurring on the study shall be documented and the Sponsor and IEC/IRB informed.

Patients clinically suspected of NASH will be invited for a screening programme for inclusion in the study. Patients will be screened according to the inclusion and exclusion criteria. Clinical evaluation will be conducted for baseline characteristics and anthropometry measurements such as body weight and height.

After clinical evaluations, all baseline safety and efficacy parameters will be recorded as per Table 1. All laboratory collections will be performed following overnight fasting (at least 8 hrs).

Following confirmation of all clinical and laboratory inclusion and exclusion criteria, patients will continue into the screening period. During the screening period liver biopsy will be performed. However, if a biopsy was performed within 6 months the slides and biopsy material, or block, must be made available for baseline documentation. Such Patients, whose historical biopsy report is available, should not use medication suspected of having an effect on NASH from the 3 months prior to the screening.

	Approved by: [name] [name]	Protocol No.: SARO.17.004.02.PROTOCOL Version No.: 2.0
---	------------------------------------	---

 Zydus Discovery DMCC	CLINICAL TRIAL PROTOCOL Saroglitazar Magnesium – Phase 2 SARO.17.004	CONFIDENTIAL Page 47 of 76
--	---	---

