If the patient has consumed restricted medications but is otherwise considered eligible to be enrolled into this study by the PI, a minimum of 1 month wash out period would be instituted before the screening visit.

Liver biopsy will be performed to confirm the diagnosis of NASH and record a baseline NAFLD Activity Score (Appendix 2). The histological evidence of NASH is defined as NAS  $\geq$  4 with a minimum score of 1 for all of its three components [steatosis, hepatocyte ballooning, and lobular inflammation].

Following confirmation of inclusion/exclusion criteria and upon histological confirmation of NASH by liver biopsy, patients will be enrolled into the study.

Eligible patients will be randomly assigned to receive Saroglitazar Magnesium 2 mg or 4 mg or placebo in a 2:2:1 ratio for 24 weeks.

Upon completion of 24 weeks of treatment, liver biopsy will be performed and the NAFLD Activity Score recorded (Appendix 2).

The scheduled visits during this study will be as follows:

- Visit 1: Screening Visit [-4 Week (-28 Days)],
- Visit 2: Enrollment Visit (Day 1  $\pm$  7 Days/Week 0),
- Visit 3: Day 43/Week 6  $\pm$  7 Days,
- Visit 4: Day 85/Week 12  $\pm$  7 Days,
- Visit 5: Day 127/Week 18  $\pm$  7 Days,
- Visit 6: Day 169/Week 24  $\pm$  7 Days,
- Visit 7: Follow-up Visit: Day 197/Week 28  $\pm$  7 Days,

Patients will be advised to follow a stable lifestyle. No change in the intensity of lifestyle (Diet/Exercise) will be allowed during the period of study. Patients will be monitored for safety and efficacy parameters as per Table No 1.

If further investigations are required in case of any AE, Investigator is advised to assess the AE and take necessary action, if required. Patients are advised to contact the Investigator for any complaints.

	Approved by: [name] [name]	Protocol No.: SARO.17.004.02.PROTOCOL Version No.: 2.0
---	---	---

 Zydus Discovery DMCC	CLINICAL TRIAL PROTOCOL Saroglitazar Magnesium – Phase 2 SARO.17.004	CONFIDENTIAL Page 48 of 76
---	---	---

[figure not shown]

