## 7.2 STUDY PROCEDURES AT EACH VISIT

### Visit Schedule

- **Screening Visit 1 [Week -4 (-28 days)]**
  - a. All patients will be required to sign and date the IRB/IEC approved ICF after all study-related procedures have been explained by the PI/designee and understanding the contents.
  - b. The informed consent process will be documented in the Source Documents, ICF and other relevant logs and signed and dated by the Investigator or delegated study team members on site. Prior to subject participation in the study, written informed consent will be obtained from each subject according to the regulatory and legal requirements of the participating country, including state-specific requirements.
  - c. Patients will be screened for eligibility; those qualifying will be invited to participate in the study.
  - d. Demographics, vitals, physical examination, medical history, prior and concomitant medication review will be recorded.
  - e. Clinical evaluation will be done for baseline characteristics and body weight will be recorded.
  - f. After clinical evaluations, all baseline safety and efficacy parameters will be assessed as per Table 1. All laboratory investigations will be performed on overnight fasting blood samples. Electrocardiograph (ECG) will be performed.
  - g. Serum pregnancy test will be done for females of child-bearing potential.
  - h. Patients are advised to maintain a stable life-style.
  - i. Adverse events will be recorded.

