## 9.4 PROCEDURES

### 9.4.1 Adverse Events

All AEs occurring during the course of the clinical study from the signing of the informed consent onwards will be collected, documented and reported to the Sponsor by the PI or designee according to the specific definitions and instructions detailed in this section. The Common Terminology Criteria for Adverse Event (CTCAE) (Version 4.03 or higher) system will be used for reporting and grading AEs.

An AE is defined as any untoward medical occurrence in a clinical investigation subject administered a pharmaceutical product and which does not necessarily have a causal relationship with this treatment.

Any medical condition already present at screening should not be reported as an adverse event unless the medical condition or signs or symptoms present at baseline changes in severity or seriousness at any time during the study. In this case, it should be reported as an adverse event.

Clinically significant abnormal laboratory or other examination (e.g. electrocardiogram) findings that are detected during the study or are present at screening and significantly worsen during the study should be reported as AEs. The PI will exercise his or her medical and scientific judgment in deciding whether an abnormal laboratory finding or other abnormal assessment is clinically significant. Clinically significant abnormal laboratory values occurring during the clinical study will be followed until repeat tests return to normal, stabilize, or are no longer clinically significant. Any abnormal test that is determined to be an error does not require reporting as an AE.

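### The washout of restricted drugs is scheduled before the only consent step and before adverse event collection, and the 30-day medication window by itself may miss the date the drug was stopped

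*Protocol*

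**What the plan says.** The washout rule appears three times in the protocol with the same timing. Section 4 says "then a minimum of 1 month wash out period will be instituted before the screening visit". The Methodology part of the summary says "a minimum of 1 month wash out period will be instituted before the screening visit". Section 7.1 repeats it: "a minimum of 1 month wash out period would be instituted before the screening visit". In each place the trigger is the investigator's view that the patient could otherwise be enrolled.

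On consent, section 7.1 states: "Informed consent will be obtained before the start of any study related procedures". The visit schedule, in the summary and in section 7.2, puts the signature at item a of Screening Visit 1: "All patients will be required to sign and date the IRB/IEC approved ICF after all study-related procedures have been explained". That visit is at Week -4 (Day -28). The visit list contains no pre-screening or washout visit.

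On safety, section 9.4.1 states: "All AEs occurring during the course of the clinical study from the signing of the informed consent onwards will be collected". SAE reporting in section 9.4.2 also runs from signature of consent. The SAP's listing of pre-treatment AEs (section 7.3.2) begins at the same point.

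On medication, section 5.8.1 requires the CRF to hold "All concomitant medications and any changes in the dosage or regimen of a concomitant medication for the 30 days preceding Visit 1", continuing to the end of the study. Separately, inclusion criterion 7a requires, for patients with type 2 diabetes, "no changes in oral agents or dose for at least 3 months before screening". Inclusion criterion 4 sets 3 months free of drugs suspected of affecting NASH for patients using a historical biopsy.

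**The concern.** A washout started because an investigator judges that the patient could then be enrolled is done for the trial. If it comes before the visit at which consent is signed, the patient gives up a glucose-lowering or NASH-directed drug for the trial without having consented to it.

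Safety recording has the same gap. An event that begins during washout falls before AE and SAE collection. If it is still present at Visit 1, section 9.4.1 treats it as a pre-existing condition, reportable only if its severity or seriousness later changes. The extra route in section 9.4.2 for SAEs outside the reporting window covers only events judged related to the sponsor's product, which these patients have not yet received.

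The stop date also matters to anyone interpreting baseline histology, liver enzymes, lipids or insulin resistance, because the restricted list is made up of drugs that affect insulin resistance or are claimed to treat NASH.

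**Working it through.** **1. Does the stated study period leave room for a washout after consent?** Inputs: Visit 1 at Week -4 and Visit 7 at Day 197 (protocol section 7.1); study duration 32 weeks (protocol summary); 4-week screening, 24-week treatment and follow-up 4 weeks after treatment (SAP section 2.2.1).

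Duration = 4 + (197 - 1)/7 = 4 + 28 = 32 weeks. This reproduces the stated figure and agrees with 4 + 24 + 4 = 32. The whole period is used up, so the washout lies outside it.

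**2. Where does the washout fall?** Let m be the washout in days. With Visit 1 at its nominal Day -28, the washout starts at Day -28 - m. The section 5.8.1 window opens 30 days before Visit 1, so the stop precedes the window by m - 30 days. If the washout were counted as study time, duration would be 32 + m/7 weeks. The protocol does not give a month in days, so 28, 30 and 31 are assumptions. The longer values illustrate an open-ended minimum.

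| m (days) | Washout starts | Stop relative to 30-day window | Duration if counted (weeks) |
|---|---|---|---|
| 28 | Day -56 | 2 days inside | 36.0 |
| 30 | Day -58 | on the edge | 36.3 |
| 31 | Day -59 | 1 day outside | 36.4 |
| 42 | Day -70 | 12 days outside | 38.0 |
| 60 | Day -88 | 30 days outside | 40.6 |
| 90 | Day -118 | 60 days outside | 44.9 |

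**3. What is and is not recorded?** The schedule puts consent at Day -28, so for a washout of about one month the 28 to 31 days before it have no AE or SAE collection. Medication recording does reach back before consent. The 30-day window covers up to the last 30 days of the washout, and may or may not include the stop itself. The other routes state no look-back limit: prior-medication review at Visit 1 (section 7.2, item d), medication history (section 6.1.2) and its place among the data reported on the eCRF (section 9.2.3). SAP section 5 also plans a listing of prior medications with start and stop dates.

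**4. How does the washout sit beside the 3-month rules?** Criteria 4 and 7a apply in addition to the washout. A diabetic patient who stopped an oral glitazone one month before screening still fails 7a. A patient with a historical biopsy who stopped a drug suspected of affecting NASH one month before screening still fails criterion 4. The washout passages mention neither rule.

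**The case against.** The strongest reply is that the protocol does not authorise withdrawal without consent. Its general rule puts consent before any trial procedure, so if the washout is such a procedure, sites must already obtain consent first. The washout text also fixes its timing against the visit and not against the signature, and prior use of a restricted drug may mean only that screening waits. Part of this stands: the documents should not be read as permitting unconsented withdrawal. But the washout is something to be instituted, which is more than waiting, and the general rule gives sites no scheduled point at which to consent earlier. The rescreening route in section 4.4.1 does not supply one. It needs sponsor approval, is described for narrow-margin failures, and is not mentioned in the washout passages. The flow chart and schedule table could not be read in the text available. If they show an earlier consent step, the visit lists disagree with them and still need correction.

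Several stronger readings are tempting, and the documents do not support them.

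- A reader might infer that the stopped drug never reaches the CRF, or that analysts cannot identify these patients. The prior-medication review, the medication history on the eCRF and the SAP listing with stop dates all contradict that.
- A reader might infer that harm during washout is wholly unrecorded. Medical history, laboratory tests and ECG at Visit 1 follow the washout and may show it, though not as an AE.
- A reader might see a flat contradiction with criterion 7a. It is a separate, cumulative criterion, and a longer gap can satisfy both.
- A reader might expect withdrawal rebound to appear as change from baseline. No passage gives a rebound time course.
- A reader might express one such patient as a share of a small arm. The documents give no expected number of patients needing washout, so that share measures nothing.

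**Conclusion.** The point holds as an inconsistency of sequence. Three passages place a trial-driven washout before the screening visit, the visit schedule places the only consent step at that visit, and AE and SAE collection begins at consent. This conflicts with the rule of consent before any trial procedure, and sites following the schedule literally would break that rule.

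The size is at least about 28 to 31 days without consent or AE/SAE collection for each affected patient, assuming a one-month washout and Visit 1 at its nominal day. The number of such patients is unknown. The medication gap is narrower: the 30-day window alone does not assure capture of the stop date once the washout lasts longer than 30 days, but other records may hold it. No endpoint, sample size or planned analysis figure is affected. The case for change rests on patient protection and complete safety recording.

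**What to change.** Reconcile the washout wording in the protocol summary, section 4 and section 7.1 with the consent rule in section 7.1, the Visit 1 procedures in section 7.2 and the AE start in section 9.4.1. Consent should be signed, and AE collection should begin, before any washout undertaken for the trial. Section 9.4.1 already ties collection to the signature, so moving the signature moves the collection with it.

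Require the restricted drug and its stop date in the CRF for every patient who has a washout, whether or not the date falls within the 30 days of section 5.8.1.

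Update the stated 32-week duration for these patients: about 36 weeks or more, if the washout is about one month.

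State how the 1-month washout fits with the 3-month rules in inclusion criteria 4 and 7a. Which period applies is for the sponsor to decide.

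The cost is protocol wording and one earlier consent contact for patients who need washout, with about a month more of recorded participation for them and a little extra medication data entry.

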## 7.2 STUDY PROCEDURES AT EACH VISIT

### Visit Schedule

- **Screening Visit 1 [Week -4 (-28 days)]**
  - a. All patients will be required to sign and date the IRB/IEC approved ICF after all study-related procedures have been explained by the PI/designee and understanding the contents.
  - b. The informed consent process will be documented in the Source Documents, ICF and other relevant logs and signed and dated by the Investigator or delegated study team members on site. Prior to subject participation in the study, written informed consent will be obtained from each subject according to the regulatory and legal requirements of the participating country, including state-specific requirements.
  - c. Patients will be screened for eligibility; those qualifying will be invited to participate in the study.
  - d. Demographics, vitals, physical examination, medical history, prior and concomitant medication review will be recorded.
  - e. Clinical evaluation will be done for baseline characteristics and body weight will be recorded.
  - f. After clinical evaluations, all baseline safety and efficacy parameters will be assessed as per Table 1. All laboratory investigations will be performed on overnight fasting blood samples. Electrocardiograph (ECG) will be performed.
  - g. Serum pregnancy test will be done for females of child-bearing potential.
  - h. Patients are advised to maintain a stable life-style.
  - i. Adverse events will be recorded.

#### **Liver biopsy Visit**

- a. Liver biopsy will be done after the patient passes all other inclusion and exclusion criteria to confirm NASH diagnosis and record a baseline NAFLD Activity Score (Appendix 2). If biopsy is done within 6 months, the slides, biopsy material or block should be available for baseline documentation. Such patients, whose historical biopsy

	Approved by: [name] [name]	Protocol No.: SARO.17.004.02.PROTOCOL Version No.: 2.0
---	------------------------------------	---

 Zydus Discovery DMCC	CLINICAL TRIAL PROTOCOL Saroglitazar Magnesium – Phase 2 SARO.17.004	CONFIDENTIAL Page 49 of 76
--	---	---

report is available, should not use medication suspected of having an effect on NASH from the 3 months prior to the Screening.

- b. Liver biopsy will be performed with a 16 gauge (1.6 mm) needle with Ultrasound guidance. The length of the specimen collected should be approximately 1.5 cm. The specimen will be read centrally for NAFLD Activity Score by pathologist at Virginia Commonwealth University, Medical Center, [name] United States.

- **Visit 2 Enrollment Visit [Week 0, Day 1+/- 7 Days]**

- a. Patients satisfying the inclusion and exclusion criteria will be randomly assigned to receive Saroglitazar Magnesium 2 mg or 4 mg or placebo.
- b. Patients will undergo physical examination.
- c. Concomitant medications will be assessed.
- d. Vitals signs will be recorded.
- e. Body weight will be recorded.
- f. ECG will be performed.
- g. Adverse events will be recorded.
- h. Urine pregnancy test will be performed for females of child-bearing potential.
- i. Safety and efficacy parameters will be assessed as per Table 1.
- j. A 6-week supply of investigational product will be dispensed (42 tablets + 7 tablets for one week allowance).
- k. Patients are advised to maintain a stable life-style.

- **Visit 3 [Day 43 (+/- 7 Days)]**

- a. Patients will undergo physical examination.
- b. Vitals signs will be measured.
- c. Body weight will be recorded.
- d. Medication compliance and concomitant medication will be assessed.
- e. A 6-week supply of investigational product will be dispensed (42 tablets + 7 tablets for one week allowance).
- f. Safety and efficacy parameters will be assessed as per Table 1.
- g. Adverse events will be recorded.

	Approved by: [name] [name]	Protocol No.: SARO.17.004.02.PROTOCOL Version No.: 2.0
--	------------------------------------	---

 Zydus Discovery DMCC	CLINICAL TRIAL PROTOCOL Saroglitazar Magnesium – Phase 2 SARO.17.004	CONFIDENTIAL Page 50 of 76
--	---	---

- h. Urine pregnancy test will be performed for females of child-bearing potential.
- i. Patients will be advised to maintain a stable lifestyle.
- **Visit 4 [Day 85 (+/- 7 Days)]**
  - a. Patients will undergo physical examination.
  - b. Vitals signs will be measured.
  - c. Body weight will be recorded.
  - d. Medication compliance and concomitant medication will be assessed.
  - e. ECG will be performed.
  - f. A 6-week supply of investigational product will be dispensed (42 tablets + 7 tablets for one week allowance).
  - g. Safety and efficacy parameters will be assessed as per Table 1.
  - h. Adverse events will be recorded.
  - i. Urine pregnancy test will be performed for females of child-bearing potential.
  - j. Patients will be advised to maintain a stable lifestyle.
- **Visit 5 [Day 127 (+/- 7 Days)]**
  - a. Patients will undergo physical examination.
  - b. Vitals signs will be measured.
  - c. Body weight will be recorded.
  - d. Medication compliance and concomitant medication will be assessed.
  - e. Safety and efficacy parameters will be assessed as per Table 1.
  - f. A 6-week supply of investigational product will be dispensed (42 tablets + 7 tablets for one week allowance).
  - g. Adverse events will be recorded.
  - h. Urine pregnancy test will be performed for females of child-bearing potential.
  - i. Patients will be advised to maintain a stable lifestyle.
- **Visit 6 [Day169 (+/- 7 Days)]**
  - a. Patients will undergo physical examination.
  - b. Vitals signs will be measured.
  - c. Body weight will be recorded.
  - d. Medication compliance and concomitant medication will be assessed.

	Approved by: [name] [name]	Protocol No.: SARO.17.004.02.PROTOCOL Version No.: 2.0
--	------------------------------------	---

- e. ECG will be performed.
- f. Liver biopsy will be performed to record final NAFLD Activity Score (Appendix 2).
- g. Safety and efficacy parameters will be assessed as per Table 1.
- h. Adverse events will be recorded.
- i. Serum pregnancy test will be performed for females of child-bearing potential.
- j. Patients will be advised to maintain a stable lifestyle.

• **Visit 7 Follow-Up Visit [Day 197 (+/- 7 Days)]**

- a. Patients will undergo physical examination.
- b. Vitals signs will be measured.
- c. Body weight will be recorded.
- d. Concomitant medication will be assessed.
- e. ECG will be performed.
- f. Safety parameters will be assessed as per Table 1.
- g. Adverse events will be recorded.

